### **3.1.5 Video Sub-Study Treatment Phase (start of the study intervention)**

Parents and their infant who are enrolled to participate in the video recorded task will be observed during an unstructured reading task, using both an e-book and a standard book, in a pre-scheduled visit, outside of their primary care visits. They will not receive any additional instruction at this visit. Parents will also participate in a brief, semi-structured interview following the reading task.

### **3.2 Allocation to Treatment Groups and Blinding**

Participants will be stratified by clinic site and randomized to receive literacy promotion using 1) standard early reader board books or 2) digital electronic early reader e-books. Randomization sequences will be developed by the study team using computer-generated random numbers prior

to study enrollment and will be placed in sealed opaque envelopes, assigning participants to one of the two treatment arms.

Participants in the video sub-study will also be randomized to determine the order in which they are asked to read the three versions of the selected book (print, basic e-book, enhanced e-book). As with the larger trial, randomization sequences will be developed by the study team using computer-generated random numbers prior to study enrollment and will be placed in sealed opaque envelopes, assigning participants to receive one of the six possible orders of the three book types.

### **3.3 Study Duration, Enrollment and Number of Sites**

#### **3.3.1 Duration of Study Participation**

The study duration for the randomized control trial per subject will be approximately 7 months following enrollment. The study duration for the video sub-study will be one day of participation.

#### **3.3.2 Total Number of Study Sites/Total Number of Subjects Projected**

The randomized control trial will be conducted at three CHOP Care Network Practices: 1) Roxborough, located in Philadelphia, Pennsylvania, 2) Indian Valley located in Souderton, Pennsylvania and 3) Cobbs Creek, located in Philadelphia, Pennsylvania. These sites have been individually recruited to participate (see PeRC letter of support) and have agreed to participate.

Recruitment for the randomized control trial will stop when approximately 100 subjects (100 dyads of parent and infant) are enrolled. Recruitment for the video-taped component will stop when approximately 40 participants have completed the video and interview task.

### **3.4 Study Population**

#### **3.4.1 Randomized Control Trial**

##### **3.4.1.1 Inclusion Criteria**

- 1) English or Spanish speaking
- 2) Child who is between 5 months 0 days and 7 months 0 days at time of enrollment and born  $\geq$  35 weeks estimated gestational age.
- 3) Parent (if mother) must be 15 years or older at the start of the study. Parent (if father) must be 18 years or older at the start of the study.
- 4) Parental permission for the child's participation and consent of the parent for their participation
- 5) Child with Medicaid Insurance

- 6) Parent has access to a smartphone and/or tablet

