### **1.2 Name and Description of Investigational Product or Intervention**

The intervention will be an adapted version of the Reach Out and Read (ROR) Program, a national program that promotes parent-child reading activities for children 6 months through 5 years of age at pediatric well child visits. It will be adapted for use with parents of children from 5 to 18 months, 30 days. Digital literacy promotion will consist of the provision of developmentally appropriate standard and digital books selected specifically for all well visits from 5 months of age onwards. In this instance we define standard as the use of age appropriate board books in literacy promotion initiatives and digital as the use of mobile app based e-book versions of the same board books. It will also include follow-up contact with the parent to ascertain whether or not they encountered issues with the apps functioning, reminders to schedule and/or attend upcoming well visits, and for some parents, an interview and video recorded reading task with their infant.

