## **3 INVESTIGATIONAL PLAN**

### **3.1 General Schema of Study Design**

#### **3.1.1 Randomized Control Trial**

We propose to test the effects of digital versus standard literacy promotion using a randomized controlled trial design. One-hundred eligible parent-child dyads, with infants between 5 and 7 months of age, who present to one of the three CHOP Care Network practices (Cobbs Creek, Roxborough and Indian Valley) will be recruited and consented to participate in this 18-month long study. Participants will be stratified by clinic site and randomized to receive literacy promotion using 1) standard early reader board books or 2) digital electronic early reader e-books. Randomization sequences will be developed by the study team using computer-generated random numbers prior to study enrollment and will be placed in sealed opaque envelopes.

Randomization will ensure equivalence between groups on measured and unmeasured characteristics and is considered to be the strongest protection against bias in study design.

Participants randomized to the digital arm will receive the e-book version of [name] *Hop on Pop* for the 6 month well visit, Sandra Boynton's *Barnyard Dance* for the 9 month well visit, and Margaret Wise' *Goodnight Moon* for the 12 month well visit. Additionally they will receive information on the importance of early parent-child reading activity by pediatric clinicians using the Reach Out and Read framework. The appropriate e-books will be electronically gifted to the participants. Parents must have an appropriate mobile digital device such as a smart phone or tablet to download and open the digital e-books.

Participants randomized to the standard arm will receive the board book versions of [name] *Hop on Pop* for the 6 month well visit, Sandra Boynton's *Barnyard Dance* for the 9 month well visit, and Margaret Wise' *Goodnight Moon* for the 12 month well visit. Furthermore, participants will be provided information on the importance of parent-child reading activity by pediatric clinicians using the Reach Out and Read framework.

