### **3.1.4 Randomized Controlled Trial Treatment Phase (start of the study intervention)**

Once recruited and enrolled, the parent-child dyads will be randomized into either the digital or standard literacy arm. Parent-infant dyads randomized to the digital literacy arm will receive the digital e-book version of [name] *Hop on Pop* for the 6 month well visit, Sandra Boynton's *Barnyard Dance* for the 9 month well visit, and Margaret Wise' *Goodnight Moon* for the 12 month well visit. Moreover, they will receive information on the importance of early parent-child reading activity by pediatric clinicians. Information on early literacy will be standardized and age-based and will be provided to parents by pediatric clinicians at the well visits.

Parent-infant dyads randomized to the standard literacy arm will receive [name] *Hop on Pop* for the 6 month well visit, Sandra Boynton's *Barnyard Dance* for the 9 month well visit, and Margaret Wise' *Goodnight Moon* for the 12 month well visit. In addition, they will be provided information on the importance of parent-child reading activity by pediatric clinicians.

Information on early literacy will be standardized and age-based and will be provided to parents by pediatric clinicians at the well visits. This conforms to the ROR National Program recommendations and is considered standard of care at these 3 clinics.

To prevent contamination in which pediatric clinicians inadvertently provide books and instruction on reading activity to the different arms of the study, an automated alert will appear on the screen of the eligible child's EHR at each well visit with a reminder to the health professional. This will ensure that books and reading instructions are consistent with their assigned study arm. Phone call or text message reminders will be used throughout the course of the study. The initial reminder will be made within the first week to participants in the digital literacy arm to verify that the participant was able to download the e-book if this was not already confirmed during the initial visit. Another reminder will be sent out about 1 month after the infant has, or is age-eligible for, their 6, 9 and 12 month well visit, either to remind the participant to complete the emailed REDCap survey, or for other study-related reminders.

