### 6.3 Statistical Methods

Summary statistics will be obtained, and differences between digital and standard arms will be assessed using intention-to-treat analysis. Cross-sectional differences in StimQ scores between digital and standard groups at the 6, 9 and 12 month well visits will be assessed using t-tests. To determine how the effects of digital versus standard literacy is associated with language development, we will develop regression models using longitudinal data methods that adjust for correlation in BSID-III scores over time and for potential confounding by demographic characteristics. To explore the impact of digital literacy on healthcare utilization, the EHR will be reviewed to identify a subjects' number of well visits and their vaccination history.

To determine whether parent adversity, health literacy, and/or parent mental health modify the effects of digital versus standard literacy on language development, we will develop similar regression models using longitudinal data methods, but we will also fit interaction terms between study group and ACE score ( $\geq 4$ ), SAHL (high or low) and EPDS score ( $> 10$ ). To determine if parent-child reading activity mediates the association of intervention group assignment and language development, we will use mediation analysis with separate models regressing group assignment on language development, parent-child reading activity on group assignment, and group assignment on language development adjusted for parent-child reading activity.

Assuming a mean cognitive subscale on the BSID-III of 96, a power of 0.70, an alpha of 0.05, and a clinically significant difference of 7.5 points on the BSID-III between groups, we estimate that we will need to recruit a total sample size of 100 eligible children (50 in each group) to participate in the main RCT study (Figure 1). To attain thematic saturation in the Video Sub-study, we will recruit up to 40 participants 9-12 months of age. These 40 participants may be recruited external to the main study if we are unable to recruit up to 40 from the 100 enrolled in the main study in a timely fashion. All analyses will be conducted using Stata Statistical Software, version 13 (College Station, TX).

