## **8.4 Recruitment Strategy**

### **8.4.1 Randomized Control Trial**

We will have an EHR recruitment prompt sent only to potentially eligible children with Medicaid at their 4 month well visit at the CHOP Primary Care Roxborough, PA, CHOP Primary Care Cobbs Creek and CHOP Primary Care Indian Valley. Parents who are conceivably interested in participating will be contacted by research staff. Research staff will briefly explain the study procedures, guided by the information set forth in the approved consent form. This includes reading the inclusion criteria to the potential participant, and asking whether or not this individual is interested in participating. Research staff will then schedule a time to meet with the parent in person. This will happen at a time before their infant's 6 month well visit in order to obtain informed consent, confirm that all of the inclusion criteria are met, and randomize the

participant into either the digital or standard book group. In the event that the research staff is unable to confirm that all inclusion criteria are met after the participant has been enrolled, the participant will no longer be able to participate. Additionally, potentially eligible 5 to 7 month olds that have been identified by study staff on EPIC as potentially eligible by screening via review of the medical record, may be approached in person before or at the time of their 6 month well visit. These potentially eligible participants will be screened, consented and enrolled into the study prior to the child's time with the provider.

We may also hang recruitment flyers in the hallways at both clinics giving information about the study and contact information for the study coordinator in case they are interested and we miss their names in the screening process.

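### The device criterion is looser than the digital arm requires and capability is checked only after assignment, so some digital-arm families may be unable to open the e-books

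*Combined protocol and SAP*

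**What the plan says.** The device criterion for the randomised trial, item 6 in section 3.4.1.1, is "Parent has access to a smartphone and/or tablet". The description of the digital arm in section 3.1.1 asks for more: "Parents must have an appropriate mobile digital device such as a smart phone or tablet to download and open the digital e-books".

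Section 8.4.1 uses the in-person meeting before the 6 month well visit to obtain consent, to "confirm that all of the inclusion criteria are met, and randomize the" participant. Section 3.1.4 then describes a first reminder to digital-arm participants, within a week, to "verify that the participant was able to download the e-book if this was not already confirmed during the initial visit". Section 1.2 adds "follow-up contact with the parent to ascertain whether or not they encountered issues with the apps functioning", and section 5.1.9 lists a text reminder about downloading, for the digital arm only. No section says what happens if the e-book cannot be made to work.

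Two further rules bear on such a family. Section 8.4.1 says that if staff are "unable to confirm that all inclusion criteria are met after the participant has been enrolled, the participant will no longer be able to participate". Section 6.3 says that "differences between digital and standard arms will be assessed using intention-to-treat analysis".

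**The concern.** A family can satisfy criterion 6 and still fall short of what section 3.1.1 expects. Criterion 6 is what staff confirm before randomising, so the functional requirement has no step at which it is enforced before assignment.

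Board books have no comparable technical barrier, so this kind of failure can arise in one arm only. Under intention-to-treat, a digital-arm family without a usable e-book stays in that arm. The comparison of e-books with board books then becomes a comparison of board books with a mixture, and that mixture can shrink a real difference or produce an apparent one against e-books.

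There is a second risk. If staff treated a later device failure as an inclusion criterion that could not be confirmed, the removal rule in section 8.4.1 would take families out of the digital arm only, and the arms would no longer be comparable by randomisation. The plan does not say which rule applies.

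**Working it through.** **Order of events.**
1. Before randomisation, section 8.4.1 confirms the listed criteria. Criterion 6 does not mention downloading or opening anything.
2. Assignment follows at the same meeting.
3. The download check in section 3.1.4 is addressed to digital-arm participants. Whether it is done at the initial visit or within the first week, it presupposes assignment.
4. The measures in sections 1.2 and 5.1.9 come later still.

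So no described step establishes before assignment that a device can run the e-books.

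**The plan's own sample size.** Inputs are a difference of 7.5 points, alpha 0.05, power 0.70 and 50 per arm (section 6.3), and SD 15 (Figure 1). Sidedness is not stated.
- n per arm = 2 × (1.96 + 0.524)² × (15/7.5)² = 49.4, rounded up to 50, so 100 in total. The plan's figure reproduces with a two-sided test; a one-sided test would give 76.
- SE = 15 × √(2/50) = 3. Power = Φ(7.5/3 − 1.96) = Φ(0.54) = 0.705.
- No allowance is stated for families who do not receive a usable book.

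**Effect of non-receipt.** Let f be the share of the digital arm unable to open the e-books. Let δ be the true board-book minus e-book difference, and d the board-book mean minus the mean of the families who cannot open them. The expected difference is (1 − f)δ + f·d. The documents give neither f nor d, so the values below are assumptions.

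*Dilution (d = 0).* The difference becomes 7.5(1 − f), and power is Φ(7.5(1 − f)/3 − 1.96):

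| f | Difference | Power at 50 per arm | Total N for 70% power |
|---|---|---|---|
| 0 | 7.5 | 0.705 | 100 |
| 5% | 7.125 | 0.661 | 110 |
| 10% | 6.75 | 0.614 | 122 |
| 20% | 6.0 | 0.516 | 156 |

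*Apparent disadvantage (δ = 0, d > 0).* The expected difference is f·d in favour of board books. If d were 7.5, this would be 0.375, 0.75 or 1.5 points at f = 5%, 10% or 20%, which is at most half of the standard error of 3. The power table does not describe this case.

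*Removal from the digital arm only.* SE = 15 × √(1/50 + 1/(50(1 − f))). Power for 7.5 points is 0.69, 0.68 or 0.65 at the same three rates. Power suffers little here; the harm is the loss of the randomised comparison.

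**The case against.** The case against has five parts.

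- **Safeguards exist.** Download can be confirmed at the initial visit, and there is contact within a week, follow-up on app problems and text reminders. A failed first attempt need not mean losing all three titles, which are supplied separately. This stands as partial mitigation, but every step comes after assignment and none provides a fallback.
- **The mismatch is thin.** Section 3.1.1 names the same kinds of device as criterion 6. That is so, but it adds what the device must be able to do, and that part is missing from the criterion.
- **The question may be pragmatic.** Section 2.1 compares digital with standard literacy promotion, so failure to open a gifted e-book could be counted as part of the strategy's effect. This is the strongest argument. It does not settle the matter, because section 3.1.1 already intends families with a capable device.
- **Non-receipt is not confined to one arm.** Section 4.2 has clinicians give books at well visits, so a missed visit could leave a board-book family without one. This is true, but the technical barrier remains specific to the digital arm.
- **The rates are assumed and the direction is open.** Both are correct. If board books are truly better and families without a working e-book do worse than e-book readers, the observed difference grows and power rises.

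A reader might go further and infer that the digital arm does contain families who receive nothing. The documents do not support that. They show a route to non-receipt, with no occurrence or rate, and digital-arm families still receive the Reach Out and Read guidance from their clinicians (sections 3.1.1 and 3.1.4).

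**Conclusion.** The point holds as a gap in design and wording. Criterion 6 is weaker than the requirement in section 3.1.1, capability is not checked before randomisation, and the plan does not say how a later failure is handled. The digital arm may therefore include families who cannot open the e-books.

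The size is unknown. The fall in power from about 0.70 to 0.66, 0.61 or 0.52 rests on assumed non-receipt of 5%, 10% or 20%, a two-sided test, SD 15, all 50 per arm analysed, and affected families scoring on average like the board-book arm. It is an illustration of dilution and not a forecast; it does not measure an apparent disadvantage for e-books. The sample size arithmetic itself is sound. The defect is not fatal, but it is worth correcting because the trial starts at only 0.70 power and prevention is cheap.

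**What to change.** - **Reword criterion 6** to match section 3.1.1: the parent has regular use of a smartphone or tablet able to download and open the study e-books.
- **Check every dyad's device before the envelope is opened**, as part of the eligibility confirmation in section 8.4.1. Compare it with the study apps' requirements: operating system, free storage and app-store access. Do this identically for all dyads and without demonstrating e-books. A trial download of some other e-book would serve less well, since it may not predict whether the study apps run and would show e-book use to families later assigned to board books.
- **State the handling of later failures.** A device failure found after randomisation is not grounds for removal under section 8.4.1, and all randomised dyads are analysed as assigned. This matters more once criterion 6 is functional, because the removal rule could otherwise be read as applying to it.
- **Record book receipt in both arms** at the 6, 9 and 12 month time points, so that actual non-receipt can be reported.

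The cost is a few minutes at an existing visit. A few families with unsuitable devices would not be enrolled, so the results would apply to families with a capable device, as section 3.1.1 already intends. A single check at enrolment cannot detect a device lost or replaced before the 9 or 12 month book, so the existing follow-up contacts should stay.

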#### **3.4.1.2 Exclusion Criteria**

- 1) Children with neurodevelopmental disabilities or congenital malformation at increased risk of language delays

### **3.4.2 Video Sub-study**

#### **3.4.2.1 Inclusion Criteria**

- 1) EITHER enrolled in the randomized control trial and age-eligible for their 9 month well visit OR (for patients recruited externally) >9 months 0days, but <12 months 0 days old and born  $\geq$  35 weeks estimated gestational age
- 2) Parent (if mother) must be 15 years or older at the start of the study. Parent (if father) must be 18 years or older at the start of the study
- 3) Parental permission for the child's participation and consent of the parent for their participation
- 4) Child with Medicaid Insurance
- 5) Parent has access to a smartphone and/or tablet

#### **3.4.2.2 Exclusion Criteria**

- 1) Parent does not speak English
- 2) Children with neurodevelopmental disabilities or congenital malformation at increased risk of language delays

Subjects that do not meet all of the enrollment criteria may not be enrolled. Any violations of these criteria must be reported in accordance with IRB Policies and Procedures.

## **4 STUDY PROCEDURES**

### **4.1 Screening/Consenting Visit and Study Visit 1**

- Identify eligible 4-month old infants at the time of their well child visit using the electronic health record (EHR)
- Recruit and consent eligible parent-child dyads at or before child's 6 month well visit.
- Randomize parent-child dyads into intervention and control groups.
- Collect baseline demographic, parent adversity, and parent mental health information.

## 4.2 Study Treatment Phase

- Implement an EHR alert to remind clinicians which arm (digital or standard) the patients are in at time of well visits at 6, 9 and 12 months.
- Provide developmentally appropriate standard books or e-books and a bookmark to clinicians to give to participants at 6, 9, and 12 month well visits.
- Parents will complete measures of reading activity (StimQ and ERPQ) via REDCap survey sent to their email about 1 month subsequent to the time the child has, or is age-eligible for, their 6 and 9 month well visits.
- Phone calls and/or text messages will be made to all participants throughout the study to remind them to schedule and/or attend well visit, and for other study-related reminders.
- Selected parents will complete a videotaped reading task at a scheduled time convenient to the participant and after the participant becomes age-eligible for their 9 month well visit. For parents enrolled external to the larger randomized control trial, this will be the only study visit completed by these participants. These participants will complete the study related questionnaires, including the demographic questionnaire, the ACE, SAHL, EPDS, StimQ and ERPQ, at the time of this study visit. Participants enrolled in the sub-study (either within the RCT or externally) will additionally complete the paper-based DialogPR-I at the time of their video sub-study visit.
- Contact participant after the child has, or is age-eligible for, the 12 month well visit to schedule the second study visit.
- At the second study visit, about 1 month after the child has, or is age-eligible for, the 12 month well visit, parents will complete measures of reading activity (StimQ, ERPQ and DialogPR-I) in addition to a measure concerning depressive symptoms (EPDS), and their child will receive a developmental assessment (BSID-III) administered by the study's Early Childhood Assessor.

